COVER PAGE

Study Title: Modern Urodynamics System Efficacy (MUSE) Study

NCT: NCT05959655

Date of Document: 2023-06-28

1 Protocol Synopsis

Study Title	Modern Urodynamics System Efficacy
Short Title	MUSE Study
Study Sponsor	Bright Uro
Protocol Number	CIP-0005
Study Objective(s)	The objectives of the present study are to evaluate the feasibility, efficacy, and safety of the GUS for use in the clinic to collect vesical pressure data.
Study Design	This is a prospective, observational trial collecting vesical pressure (Pves) and flow from the GUS and cUDS system in patients with Lower Urinary Tract Symptoms (LUTS).
Phase	Phase 0
Estimated Study Period	Up to 24 months
Investigational Devices	Glean Urodynamics System (GUS)
Indications for Use/Intended Use	
Indications for Use: The GUS is indicated for standard Urodynamic tests such as Uroflowmetry (UF), Cystometrogram (CMG), Urethral Pressure Profile (UPP), and Micturition Studies (MS).
 
Intended Use: The GUS is a Urodynamic Analyzer system that is intended to quantify the pressure characteristics of the lower urinary tract. The system can be used to perform standard Urodynamic tests such as UF, CMG, UPP, and MS.
 
The major application of Urodynamics is the diagnosis of uncontrolled loss of urine (incontinence), abnormal urinary retention, or neurological cases of Micturition disorder. The device is intended to be used as medical diagnostic equipment.

Number of Subjects	Up to 50 subjects will be enrolled. Assuming a ~20% dropout rate, we expect 40 subjects (20 males and 20 females) to complete the study.
Duration of Study and Follow-up	Each subject will be in the study for up to 24 hours to complete ambulatory GUS.
Study Population	Patients with Lower Urinary Tract Dysfunction (LUTD) who are scheduled for cUDS studies.
Study Site(s)	Up to 6 sites in the United States
Inclusion Criteria	
 1. Male or female patient must be \geq 18 years of age 2. Patient must have a diagnosis of LUTD 3. Patient must be scheduled for or recommended for cUDS 4. Patient is able to tolerate 18Fr catheterization 5. Patient or patient's legally authorized representative is able to provide informed consent
Exclusion Criteria	
 1. Pregnant (as confirmed by urine pregnancy test) or breastfeeding, pregnant within the past 6 months or intend to become pregnant during the study period. 2. Patient has a symptomatic UTI based on CDC guidance (see below) 3. Subjects who, at the principal investigator's determination, would not be appropriate for this study.
Experimental Procedures	
 1. Patient screened for eligibility and enrolled at the discretion of the principal investigator. 2. A urinalysis (if positive, urine culture), uroflowmetry, and post-void residual (PVR) will be recorded prior to beginning the study. 3. At the first clinic visit, a urine sample will be collected for urinalysis and urine culture prior to any UDS procedures.

	
 4. Patient is prepared for cUDS per standard of care 5. Clinician will perform standard cUDS cystometry and pressure-flow studies per standard of care including uroflowmetry and PVR. 6. Upon completion of cUDS, the cUDS catheters are removed to allow for insertion of the Glean Sensor. 7. Clinician will gather GUS package and remove sterile pouch from outer packaging. 8. Clinician will open the Glean Clinician App on the mobile device and initiate a new patient Sensor Insertion. The tablet will prompt the clinician to scan the QR code of the GUS. 9. Clinician will scan the QR code through the transparent pouch of the packaging and pair Sensor. 10. Once paired, the Clinician removes inner packaging from sterile pouch using aseptic techniques and places it on a flat surface. 11. The Clinician prepares for aseptic insertion. 12. The Clinician instills lubricant into urethra. For patients with hypersensitivity to pain and sensor insertion, a lubricant with a local anesthetic (e.g., lidocaine) can be applied 5-10 minutes prior to cUDS catheter insertion. 13. Clinician applies lubricant to the Glean Sensor and the tip of the Glean Insertion Sheath while still in the inner packaging. 14. Clinician draws the Sensor into insertion position within the Insertion Sheath by pulling on the removal string from the proximal end of the Insertion Sheath. When positioned correctly, the Sensor will protrude from the distal end of the Insertion Sheath (no more than 1 cm). 15. The Clinician then uses the Insertion Sheath to place the Sensor in bladder. 16. The Clinician confirms Sensor's placement and removes Insertion Sheath. 17. A removal string is taped to patient's body (e.g., thigh, perineum). 18. Patient is asked to perform the following actions: sit up, stand, bend over, twist from one side to the other, jump (if possible), squat (if possible), walk (if possible), cough, and perform Valsalva maneuver ("bear down"). 19. The Patient is then trained to use the Patient Application. 20. In clinic ambulatory GUS is then collected. The patient can dress and leave the procedure room. The patient is encouraged to drink fluids to fill their bladder and to log bladder sensations using the Patient Application. 21. During this period, the patient will complete study surveys. 22. Upon logging sensation of a Strong Desire to Void (SDV), the patient will report back to the clinical staff to void using the Uroflowmeter. 23. Clinician will use the clinician tablet to scan the QR code on the clinic uroflowmeter and pair the clinic Uroflowmeter with the appropriate patient Sensor. 24. The patient will be instructed to void using the clinic Uroflowmeter and PVR will be measured. 25. Upon completion of void, the Uroflowmeter will transfer data to the Clinician App and data will be transferred to the Bright Uro servers. 26. The clinician will remove the Sensor by pulling on the removal string 27. The patient will then be discharged from the study.
Study Endpoints	
Baseline Characteristics and Demographics (obtained from EMR or patient chart): Age, sex, prior urological conditions, reason for UDS, LUTD-related medications
 
Primary Endpoints: Success of Glean sensor insertions and removals, subjects experiencing a device-related Serious Adverse Event (SAE), and subject exhibiting compliance in terms of device and voiding diary usage.
 
Secondary Endpoints: Participant-reported outcomes (e.g., comfort, ease of use), successful transfer of GUS data from devices to clinician App and clinician web portal for clinician review.

Analyses	Success of Glean sensor insertions and removals will be calculated as percent of insertions and removals deemed successful by the clinician and subject.

	
Safety will be reported as the percent of subjects experiencing a device-related SAE. Rates of SAEs will be calculated on a per-subject, per-event, or per-person-year of follow-up basis. Exact binomial confidence intervals will be calculated for subject-based or event-based rates.
 
Likert scale outcomes will be summarized using frequencies and distributional statistics with binomial or normal approximation-based confidence intervals.

Study and Data Management	
Bright Uro [name] [contact] [contact] [contact]

Safety Monitoring	Site Investigators

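### The objective includes efficacy in collecting vesical pressure, but no endpoint listed in the synopsis shows that a recorded pressure trace is readable

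*Combined protocol and SAP*

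**What the plan says.** All references are to section 1, Protocol Synopsis, of the combined protocol and SAP.

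- **Study Objective(s):** the aim is to "evaluate the feasibility, efficacy, and safety of the GUS for use in the clinic to collect vesical pressure data". The word efficacy also stands in the study title.
- **Study Design:** the study is described as "collecting vesical pressure (Pves) and flow from the GUS and cUDS system in patients with Lower Urinary Tract Symptoms (LUTS".
- **Number of Subjects:** up to 50 are enrolled, and after about 20% dropout "we expect 40 subjects (20 males and 20 females) to complete the study".
- **Experimental Procedures:** with the sensor in place, the subject performs posture changes, a cough and a Valsalva manoeuvre (step 18). Ambulatory recording follows (step 20): "The patient is encouraged to drink fluids to fill their bladder and to log bladder sensations using the Patient Application". At step 24, "The patient will be instructed to void using the clinic Uroflowmeter and PVR will be measured".
- **Study Endpoints, primary:** "Success of Glean sensor insertions and removals, subjects experiencing a device-related Serious Adverse Event (SAE), and subject exhibiting compliance", the compliance being with use of the device and the voiding diary.
- **Study Endpoints, secondary:** participant-reported outcomes, and successful transfer of GUS data to the clinician App and web portal so that a clinician can review them.
- **Analyses:** three paragraphs, on insertion and removal success, SAE rates, and Likert-scale items.

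**The concern.** The device exists to record bladder pressure, and the objective speaks of efficacy in doing so. The listed endpoints show that the sensor was placed and removed, that it was used, that it was tolerated, and that data arrived. They do not show that what arrived can be read as a pressure trace.

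Followed as the synopsis is written, the study could report high success on every listed item without saying how often the GUS gave a usable recording. If a usability rate were reported later, and no rule is set in text not supplied here, the definition would be chosen by people who had already seen the traces.

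**Working it through.** **1. The plan's own figure.** Inputs from Number of Subjects: 40 completers and 20% dropout. 40 / (1 − 0.20) = 50, and 50 × 0.80 = 40. The stated enrolment is reproduced. No hypothesis, margin, standard deviation or power is given, so there is no power calculation to check, and the point does not depend on one.

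**2. Endpoints and analyses side by side.**

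| Endpoint item | What it shows about collection | Uses Pves or a readability rule? | Listed analysis |
|---|---|---|---|
| Insertion and removal success | Sensor was handled successfully in the view of clinician and subject | No | Percent |
| Device-related SAE | Nothing | No | Percent and rates, exact intervals |
| Compliance | Device and diary were used | No | None specific |
| Participant-reported outcomes | Nothing | No | Likert summaries |
| Data transfer | Data were delivered for review | No | None specific |

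The count is 0 of 5 endpoint items and 0 of 3 analysis paragraphs. Flow is left out of the argument because the objective names only vesical pressure.

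**3. The closest item.** Transfer is nearest to a measure of the recording. The synopsis does not define when a transfer is successful and gives no calculation for it. A delivered file with a flat, drifting or interrupted signal is therefore not excluded from counting as a success. Step 16 has the clinician confirm placement, but states no pressure criterion for doing so.

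**4. Whether an evaluable-trace endpoint would be informative at this size.** For x evaluable of n, the Clopper-Pearson 95% limits are

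- lower = Beta quantile 0.025 with parameters (x, n − x + 1);
- upper = Beta quantile 0.975 with parameters (x + 1, n − x);
- when x = n, the lower limit reduces to 0.025^(1/n) and the upper is 100%.

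The synopsis does not say when dropout occurs, so attempted insertions are taken as between 40 and 50.

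| Denominator | Source | Result | Exact 95% interval |
|---|---|---|---|
| 40 | expected completers | 40/40 | 91.2% to 100% |
| 40 | expected completers | 36/40 (90%) | 76.3% to 97.2% |
| 50 | maximum enrolled | 45/50 (90%) | 78.2% to 96.7% |
| 20 | expected per sex | 20/20 | 83.2% to 100% |
| 20 | expected per sex | 18/20 (90%) | 68.3% to 98.8% |
| 30 | assumed number voiding | 30/30 | 88.4% to 100% |
| 30 | assumed number voiding | 27/30 (90%) | 73.5% to 97.9% |

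How many subjects will void with the sensor in place is not stated. If it were 20 (also an assumption), the 20/20 and 18/20 rows apply. These intervals describe the precision of the proposed endpoint. They do not measure the gap itself, which is the count in step 2.

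**The case against.** The best reply is that the objective concerns collecting data, and that insertion, device use and transfer for clinician review together measure collection. Part of this stands. A reader might infer that efficacy has no measure of any kind, and the documents do not support that: three of the five items bear on collection. What remains is that none of the three shows the trace to be readable, and the one closest to doing so is undefined and unanalysed.

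A second reply is that only a synopsis was supplied. Exclusion criterion 2 points to guidance below that does not appear in the supplied text, so further text may well exist and may hold a reading rule. This limits the finding to what the synopsis lists. It does not remove it, because the synopsis has its own endpoint and analysis rows and those do not match its objective.

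A third reply is that this is a Phase 0 observational study without a hypothesis. That is so, and nothing here asks for a test or a larger sample.

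A reader might also infer that the study needs an analysis of agreement between the GUS and cUDS, since the design collects pressure from both. The documents do not support that either. The objective makes no claim of agreement, and the recordings are sequential: "Upon completion of cUDS, the cUDS catheters are removed to allow for insertion of the Glean Sensor". Ambulatory filling with the GUS then relies on drinking.

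Nor do the documents show that a usability rule will be chosen after the fact. That harm arises only if a usability rate is later reported without a rule fixed in advance.

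**Conclusion.** The point holds for the synopsis. The objective includes efficacy in collecting pressure data, several endpoints measure steps towards collection, and none establishes that the recorded Pves trace can be read (0 of 5 endpoint items, 0 of 3 analysis paragraphs). Confidence is high for what the synopsis lists. It is lower for the plan as a whole, since a fuller protocol could supply the missing rule. Subject safety is not affected. The gap should be closed before any trace is read, because the data for closing it are already being collected and the planned size gives a usable estimate.

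**What to change.** Before any trace is read, make these changes to the endpoint and analysis rows.

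1. **Efficacy endpoint.** Add the proportion of subjects with attempted sensor insertion who have an evaluable GUS Pves trace, with a Clopper-Pearson 95% interval. Exact binomial intervals are already planned for SAE rates.
2. **Written reading rule, applied by existing study clinicians.** It should require a visible pressure response to the step 18 cough and Valsalva where these were performed and recorded, a minimum share of interpretable recording time, and a longest allowed gap during ambulatory filling. The sponsor sets the last two values in advance.
3. **Reasons.** Tabulate every non-evaluable case as insertion failure, no or incomplete transfer, or poor signal. Also report the proportion evaluable among transferred traces, so that signal quality is separated from the existing insertion and transfer endpoints.
4. **Void trace.** Report it separately among subjects who void with the sensor in place, with the number who did not void and why. Inability to void is then not counted as device failure. The Intended Use text names "abnormal urinary retention, or neurological cases of Micturition disorder" among the applications of urodynamics in general. It does not say how many enrolled subjects will be unable to void.
5. **Transfer.** Define success and state how it is calculated.

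**Alternative:** if the sponsor wants no pressure-data endpoint, limit the objective and conclusions to feasibility and safety. This costs only wording but gives up the efficacy claim.

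**Cost of the main fix:** wording, a short reading rule, and the reading of up to 50 traces already planned for collection, with no new subjects, visits or procedures. The readers are unblinded, which is why the rule must be fixed beforehand. The void result rests on fewer subjects and has a wider interval. The evaluable-trace figure may look less favourable than handling success alone.

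### Comfort is surveyed only after the Sensor is in place, so subjects with failed insertion or early removal have no scheduled rating and the comfort summary may be too favourable

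*Combined protocol and SAP*

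**What the plan says.** All references are to the combined protocol and SAP, section 1 Protocol Synopsis.

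- **Endpoint.** Study Endpoints lists among the secondary endpoints "Participant-reported outcomes (e.g., comfort, ease of use").
- **When it is measured.** Experimental Procedures, step 21: "During this period, the patient will complete study surveys". The period is the one opened by step 20: "In clinic ambulatory GUS is then collected".
- **What must happen first.** Step 16: "The Clinician confirms Sensor's placement and removes Insertion Sheath". The movement, cough and Valsalva manoeuvres (step 18) and training on the patient app (step 19) also come before the surveys.
- **What comes after.** Voiding on the uroflowmeter is step 24. Removal is step 26: "The clinician will remove the Sensor by pulling on the removal string".
- **How it is analysed.** Analyses: "Likert scale outcomes will be summarized using frequencies and distributional statistics with binomial or normal approximation-based confidence intervals". No denominator or rule for missing ratings is given.
- **Numbers.** Number of Subjects: "Up to 50 subjects will be enrolled", followed by "Assuming a ~20% dropout rate, we expect 40 subjects (20 males and 20 females) to complete the study". Dropout is not defined and no reasons for it are given.

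No step describes a survey for a subject in whom placement fails or whose Sensor is taken out before step 21.

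**The concern.** Comfort is rated only by subjects who have had the Sensor placed and have kept it in through the manoeuvres and app training. Someone in whom insertion was abandoned because it hurt, or who asked for the Sensor to come out, has relevant experience of the device but no scheduled occasion to report it. Whether a rating exists can thus depend on what the rating would have been.

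At stake is how the secondary result is read. A percentage of favourable comfort ratings will be taken as describing patients offered the device, when under the schedule as written it describes those who tolerated it to step 21. The planned confidence intervals express sampling error only and will not show this selection. Step 26 removes the Sensor and step 27 discharges the subject, so a rating not collected at the time cannot be reliably recovered later.

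**Working it through.** **1. The plan's own figure.** Enrolment needed for 40 completers at 20% dropout is 40 / (1 − 0.20) = 50. This matches the stated maximum, so up to 50 − 40 = 10 subjects are expected not to complete. The plan does not say when or why they leave.

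**2. Where non-completers can fall.** Reading the numbered steps in order:

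| Point of leaving | Glean insertion attempted? | Scheduled survey? |
|---|---|---|
| After enrolment (step 1), before insertion (step 15) | No | No, and there is no device experience to rate |
| During insertion (steps 15–16), or after it but before step 21 | Yes | No |
| After step 21, before the end of steps 22–26 | Yes | Yes |

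Only the middle row creates the gap. Call the number of such subjects k. The documents give no value for k. The planning figures suggest a range of 0 to 10, and 10 is reached only if every expected non-completer falls in the middle row.

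**3. Illustration.** Assumptions, none of them from the plan: 40 subjects answer the survey; 36 of them give a favourable comfort rating; k further subjects with an attempted insertion are not surveyed.

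- Reported rate: 36/40 = 90.0% (exact 95% CI 76.3% to 97.2%).
- Rate over all attempted, if all k are unfavourable: 36/(40 + k).
- Rate over all attempted, if all k are favourable: (36 + k)/(40 + k).

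| k | All k unfavourable | Exact 95% CI | Overstatement | All k favourable |
|---|---|---|---|---|
| 0 | 36/40 = 90.0% | 76.3–97.2% | 0 points | 90.0% |
| 2 | 36/42 = 85.7% | 71.5–94.6% | 4.3 points | 38/42 = 90.5% |
| 5 | 36/45 = 80.0% | 65.4–90.4% | 10.0 points | 41/45 = 91.1% |
| 10 | 36/50 = 72.0% | 57.5–83.8% | 18.0 points | 46/50 = 92.0% |

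**4. Dependence on the assumed rate.** If p is the reported rate, the worst-case overstatement is p − 40p/(40 + k) = p × k/(40 + k). At k = 10 this is 0.20 × p: 18 points at 90%, 16 at 80% and 14 at 70%.

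**The case against.** The strongest replies, and what stands of each:

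- **Failed insertions are already visible.** They count against a primary endpoint, insertion and removal success, in which the subject also has a say. This stands in part: the failures are not hidden, and it would be wrong to say that these subjects have no voice. But a success judgement is not a comfort rating and does not change the comfort denominator. A subject with a successful insertion who later asks for removal because of pain could count as a success there and be absent from the comfort data.
- **Eligibility screens them out.** An inclusion criterion requires tolerance of an 18Fr catheter. That may make k small; it does not make it zero, and it does not address discomfort with the Sensor left in place.
- **The schedule is silent, not prohibitive.** True. The survey instruments are not shown, and the text available is a synopsis. Even so, with up to 6 sites, silence leaves each to handle early stops in its own way.
- **The direction is not certain.** This stands. Glean insertion follows removal of the cUDS catheters (step 6), and residual soreness could lower Glean ratings. Subjects who stop early might also rate favourably, for instance after a purely technical failure.

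A reader might infer that the plan counts failed insertions as dropout, or that dropout in a study lasting at most 24 hours must be mostly device-driven. The documents support neither. Dropout is undefined, and because enrolment is step 1, a subject can leave during urinalysis, culture or cUDS without meeting the Sensor, or after step 21 with a rating already given.

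**Conclusion.** The gap is real. As scheduled, comfort ratings come only from subjects with the Sensor in place at step 21; there is no provision for attempted insertions that fail or end early, and no stated denominator. The comfort summary may therefore be biased upward.

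The size cannot be computed from the documents. At an assumed 90% favourable among 40 respondents, the worst-case overstatement is 4 points with 2 unsurveyed subjects, 10 with 5 and 18 with 10; it is zero if there are none. The 18-point figure should not be read as an estimate. It needs all 10 expected non-completers to have had an insertion attempted, to have left before the survey and to be unfavourable. Nor is an upward net bias established as fact, since soreness from cUDS could pull the other way.

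The endpoint is secondary and descriptive with no success threshold, so this does not threaten the study's main conclusions. It is worth correcting because the change is small and the data must be collected on the day.

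**What to change.** - **Collection.** Add a sentence to the Experimental Procedures: the comfort items go to every subject in whom Glean insertion is attempted, at step 21 for those who continue and at the time of stopping for those who do not.
- **Denominator.** State in Analyses that the comfort Likert results are reported over all subjects with an attempted insertion, with the number surveyed and the reason for each non-completion.
- **Sensitivity line.** Show the comfort result again with unsurveyed subjects who stopped for pain or intolerance counted as unfavourable. Purely technical failures should not be placed in that category automatically.
- **Ease of use.** Keep app ease-of-use items to subjects who used the app.

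Two related matters are optional. Because step 21 precedes removal, the scheduled surveys cannot capture discomfort at removal. A rating between cUDS and Glean insertion would help separate the two sources of soreness, but it adds a form for everyone and is not needed to close this gap.

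Cost: one or two sentences in the plan, a short form for the few subjects who stop early, and one extra table. The comfort figure may come out lower.

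### Does the primary compliance endpoint rest on a voiding diary that the study never collects or analyses?

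*Combined protocol and SAP*

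**What the plan says.** The Study Endpoints row of the Protocol Synopsis names three primary endpoints: insertion and removal success, device-related SAEs, and "subject exhibiting compliance in terms of device and voiding diary usage". The term voiding diary occurs nowhere else in the supplied text.

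In Experimental Procedures, the steps nearest to a diary are these:

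- Step 19: "The Patient is then trained to use the Patient Application".
- Step 20: "In clinic ambulatory GUS is then collected", and then "The patient is encouraged to drink fluids to fill their bladder and to log bladder sensations using the Patient Application".
- Step 21: "During this period, the patient will complete study surveys".
- Step 22: "Upon logging sensation of a Strong Desire to Void (SDV), the patient will report back to the clinical staff to void using the Uroflowmeter".
- Steps 23 to 25: the clinic uroflowmeter is paired with the Sensor, the void and PVR are measured, and the data are transferred.

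The Analyses row covers the first two primary endpoints: "Success of Glean sensor insertions and removals will be calculated as percent of insertions and removals deemed successful by the clinician and subject" and "Safety will be reported as the percent of subjects experiencing a device-related SAE". It adds exact binomial intervals for subject-based or event-based rates, and summaries of Likert outcomes. It does not mention compliance.

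**The concern.** Read literally, the endpoint asks for data that no listed step produces. The patient logs sensations rather than voids, and is only encouraged to do so, so no required entry exists against which to score anyone. The unit is the subject, but what makes a subject compliant is not stated, nor is the denominator.

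Two further points add to the worry. A logged strong desire to void is what sends the patient to the uroflowmeter, so logging may be close to automatic among those who finish. And in this population a missing entry could mean no sensation, an app failure or a failure to log, of which only the last is patient behaviour.

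Feasibility is the first of the stated objectives, and compliance is one of its primary measures. At stake is whether that estimate could be interpreted, or reproduced by a second analyst.

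**Working it through.** **1. The plan's own figure.** Number of Subjects gives up to 50 enrolled, about 20% dropout and 40 completing. 40 / (1 − 0.20) = 50, which reproduces. No alpha, power, margin or success threshold is given, so there is no decision rule for compliance to distort.

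**2. Endpoints against analysis sentences.**

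| Endpoint | Sentence in Analyses |
|---|---|
| Insertion and removal success (primary) | yes |
| Device-related SAE (primary) | yes |
| Compliance (primary) | none of its own |
| Participant-reported outcomes (secondary) | yes, for Likert items |
| Data transfer to app and portal (secondary) | none of its own |

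Two of the three primary endpoints have a sentence, but so does only one of the two secondary ones. The row is abbreviated throughout; compliance has not been singled out.

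**3. Endpoint against procedures.** A diary is named in 0 of 27 steps. The two halves of a diary are nevertheless covered: symptom entries by the patient (steps 19, 20 and 22) and the void itself by the uroflowmeter and PVR (step 24), with transfer in step 25. Device use is bounded by confirmed placement (step 16) and removal (step 26). The 24-hour figure under Duration of Study is a ceiling, and an in-clinic session fits inside it.

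**4. Is an analysis available?** A compliance percentage per subject is a subject-based rate, so the exact binomial sentence can supply its interval. That sentence sits in the safety paragraph, but its wording is general. For illustration, with 40 completers and assumed counts, the exact 95% intervals are:

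| Compliant | Rate | Interval |
|---|---|---|
| 32/40 | 80% | 64.4% to 90.9% |
| 36/40 | 90% | 76.3% to 97.2% |
| 40/40 | 100% | 91.2% to 100% |

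**5. What the unstated denominator could do.** Let c be compliant completers (of 40) and d compliant dropouts (of 10). Completer rate minus enrolled rate is

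c/40 − (c + d)/50 = 0.20 × (c/40 − d/10).

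| c | d | Difference |
|---|---|---|
| 40 | 0 | 20 points |
| 36 | 0 | 18 points |
| 36 | 5 | 0.20 × (0.90 − 0.50) = 8 points |
| 36 | 9 | 0.20 × (0.90 − 0.90) = 0 points |

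The values of c and d are assumptions; the documents give no compliance rate. The formula holds for any per-subject rate in the trial, including the SAE percentage, whose analysis set is also unstated. It therefore does not measure a defect peculiar to compliance.

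**The case for a change.** The strongest reply is that a descriptive study's product is its estimates, and two analysts given only this text could report different compliance figures. The app log is not called a diary anywhere. If a separate diary was intended, the listed steps collect nothing for it. The reason for a missing entry may also be hard to recover once the patient has been discharged.

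The textual part of this stands: the name is inconsistent and the compliance rule is unwritten. It does not establish a missing data source. The supplied text is a synopsis, and its exclusion criteria point forward to material not supplied, so a fuller protocol may describe the diary. If it does not, the app log is the only patient-kept record in the procedures apart from unnamed surveys, and an analyst would turn to it.

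Nor would a more elaborate definition clearly do better. One could drop subjects with no sensation or an app failure from the logging denominator. Suppose 44 subjects have a placed Sensor, 35 logged, 6 did not and 3 could not be assessed (all assumed). The rate becomes 35/41 = 85.4% instead of 35/44 = 79.5%. Removing app failures flatters the device in a feasibility study. Counting failed insertions against device compliance would repeat what the insertion endpoint already records. Scoring the strong-desire entry would choose the very measure suspected of being near automatic. These choices are debatable, and none is plainly better than a simple percentage with the reasons for missing entries listed.

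**Conclusion.** No change is needed. The omission is real: a diary named once, no procedure step using the term, and no compliance sentence in the Analyses row. It amounts to loose naming and missing detail in an abbreviated synopsis. The Patient Application log is most likely the intended diary, and a per-subject percentage with the exact interval already planned is the obvious summary. An analyst would count subjects with a placed Sensor, report device use and logging, and say why entries are absent.

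No false claim of success can follow, because no threshold is set. The spread of 0 to 20 points is a general bound from the choice of analysis set, on assumed rates, and not an expected shift.

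This rests on two assumptions that the supplied text cannot confirm: that the app log is the diary, and that analysts report the denominator they use. If a separate diary was meant, its issue and collection would have to be described in the fuller protocol.

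### Does the sensor insertion and removal success percentage need a per-subject redefinition because the plan does not state its denominator or whether the two steps are pooled?

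*Combined protocol and SAP*

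**What the plan says.** Three parts of the Protocol Synopsis bear on the point.

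- **Analyses, device success.** "Success of Glean sensor insertions and removals will be calculated as percent of insertions and removals deemed successful by the clinician and subject". The counted unit is the procedure. The sentence gives no denominator in subjects, does not say whether the steps are combined, and has no rule for repeat attempts or for disagreement between clinician and subject.
- **Analyses, safety.** "Safety will be reported as the percent of subjects experiencing a device-related SAE". Here the unit is the subject, although the next sentence also allows SAE rates per event or per person-year. The paragraph ends: "Exact binomial confidence intervals will be calculated for subject-based or event-based rates". No confidence level is given.
- **Experimental Procedures.** Step 15 is the insertion: "The Clinician then uses the Insertion Sheath to place the Sensor in bladder". Step 26 is the removal: "The clinician will remove the Sensor by pulling on the removal string". Each is described once per subject, and the second depends on the first.

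The only size statement is in Number of Subjects: "Up to 50 subjects will be enrolled", followed by "Assuming a ~20% dropout rate, we expect 40 subjects (20 males and 20 females) to complete the study". No target success rate, performance goal or power is stated.

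**The concern.** Insertion and removal are linked steps on the same subject. In a pooled percentage, a subject with both steps successful adds two successes. A subject whose insertion fails, and who therefore has no removal, adds only one failure. With one attempt per step, the pooled figure can then never be below the share of subjects in whom the sensor both went in and came out as intended, and it is usually above it. A binomial interval on the pooled count also counts most subjects twice, so it is too narrow as a statement about subjects.

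Feasibility is the first objective the synopsis names, and no performance goal is set, so this percentage is itself the main feasibility result. If the counting rule is open, the same data could be shown as 92.6%, as 90.0% with 95.6%, or as 86.0%, and the choice could be made after the data are seen. The safety endpoint has an explicit subject denominator, which makes its absence here more noticeable.

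**Working it through.** **The plan's own figure.** 40 completers at 20% dropout: 40/(1 − 0.20) = 50. The stated enrolment reproduces. It does not depend on how device success is counted.

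**Inputs.** From the documents: up to 50 subjects, and one insertion and one removal described per subject. Assumed, because the documents give none: all failure counts, a 95% confidence level, one attempt per step, and no removal after a failed insertion. Intervals are exact (Clopper-Pearson).

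**Formulas.** Let n subjects be attempted, with k failed insertions and r failed removals.

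- Pooled: (2n − 2k − r)/(2n − k)
- Insertion rate: (n − k)/n
- Removal rate among those placed: (n − k − r)/(n − k)
- Both steps successful: (n − k − r)/n
- Pooled minus both: (k + r)(n − k)/[n(2n − k)], which is never negative

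**Results.**

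| n, k, r | Pooled | Insertion | Removal | Both steps | Gap (points) |
|---|---|---|---|---|---|
| 50, 5, 2 | 88/95 = 92.6% (85.4–97.0) | 45/50 = 90.0% | 43/45 = 95.6% | 43/50 = 86.0% (73.3–94.2) | 6.6 |
| 50, 2, 1 | 95/98 = 96.9% (91.3–99.4) | 48/50 = 96.0% | 47/48 = 97.9% | 47/50 = 94.0% (83.5–98.7) | 2.9 |
| 40, 4, 2 | 70/76 = 92.1% (83.6–97.0) | 36/40 = 90.0% | 34/36 = 94.4% | 34/40 = 85.0% (70.2–94.3) | 7.1 |

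The gap under pooling is therefore real.

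**Do separate rates lose the joint share?** No. Under these assumptions the denominator of the removal rate is the numerator of the insertion rate, so the product is exact:

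- 45/50 × 43/45 = 43/50
- 48/50 × 47/48 = 47/50
- 36/40 × 34/36 = 34/40

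Neither rate alone is the joint share, but the pair with its counts is.

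**Is the pooled interval wrong for what it estimates?** With n = 50 and independent subjects, the exact probability that the pooled interval contains each target is:

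| True insertion, removal success | Contains procedure rate | Contains share with both steps |
|---|---|---|
| 0.90, 43/45 | 96.0% (rate 0.926) | 56.2% (share 0.860) |
| 0.96, 47/48 | 98.9% (rate 0.969) | 81.0% (share 0.940) |
| 0.98, 0.99 | 98.4% (rate 0.985) | 99.9% (share 0.970) |

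Even when pooled, the interval is adequate for the procedure rate. It falls short only when it is read as a share of subjects, and the shortfall depends strongly on the assumed failure rates.

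**Repeat attempts.** If every attempt is counted and 5 of 50 subjects fail twice each, insertion success is 45/55 = 81.8% of attempts against 45/50 = 90.0% of subjects. The direction of any difference is therefore not fixed.

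**The case for a change.** The best case for a change is that fixing the unit costs only wording and removes the chance to choose among several figures once data are in. The synopsis does not state the separate reading. The exact product of the two rates needs each subject to count once, so it fails if repeat attempts enter the denominators. Nor is there a rule for a clinician and a subject who disagree about success, and redefining the unit would not supply one.

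These are true statements about missing detail, and a short clarification would be harmless. They do not show that following the plan gives a wrong answer. The main numerical harm needs two things the plan does not contain: adding the two steps together, and presenting the total as a share of subjects. The contrast with safety is also weaker than it looks, because SAE rates may be given per subject or per event, and the interval sentence, although placed in the safety paragraph, names both bases. Difficulty in placing the sensor and difficulty in removing it are different device problems, so reporting them separately is legitimate and arguably more informative than a composite.

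**Conclusion.** The wording is loose, and the arithmetic behind the concern is right: pooling would exceed the share of subjects with both steps successful by 2.9 to 7.1 points in the cases above, all of which rest on assumed failure counts. The concern does not carry through to a change. One insertion and one removal per subject lead naturally to two percentages over identifiable subjects, and with counts shown these return the joint share exactly when each subject counts once.

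This is an observational feasibility study of up to 50 subjects. No hypothesis, threshold or sample-size calculation rests on the percentage, so no decision in the plan turns on the unit. Denominators, number of attempts, confidence level and handling of disagreements are details an analyst would be expected to state in the report. Making a per-subject composite the primary estimate, rather than two rates, is a matter of preference.

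The conclusion assumes that counts are reported with the percentages and that a pooled figure, if one is given, is labelled as a rate per procedure.
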